6.12.2. Delayed-Start Period

6.12.2.1. Primary Analysis

Study AZET was deemed to be futile and stopped on June 12, 2018. Because of this futility, the original analysis to test the delayed-start hypothesis to evaluate disease modification by LY3314814 assessed by ADAS-Cog₁₃ was moot. Additionally, very few patients have exposure in the Delayed-Start period. Because of the limited number of patients and exposures in the Delayed-Start period, only safety data will be summarized from this study period. No efficacy or biomarker data will be summarized from this study period. These data will be included in listings covering both the Placebo-Controlled period and the Delayed-Start period.

6.13. Safety Analyses

Safety presentations will be based on the Safety-PC and Safety-DS populations, as relevant. No between treatment p-values will be calculated for analyses of the Safety-DS population.

6.13.1. Extent of Exposure

Days of exposure will be calculated for each subject: (Date of last dose – date of first dose + 1). Summary statistics will be presented for the total number of days of exposure by treatment. Study drug treatment assignment will be listed.

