## 8.1.2. Temporary Discontinuation from Study Treatment

Treatment can be temporarily discontinued (examples include short-term treatment using a prohibited drug, uncertain adverse event, hospitalization). Re-starting investigational product is based on the Principal Investigator's judgment. The maximum permissible treatment suspension is a total of 6 weeks over the duration of the study. Temporary treatment discontinuation and restarting needs to be documented. If temporary discontinuation is due to an AE, it should be reported to the Sponsor-designated medical monitor.

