6.1.2. Delayed-Start Period

Unless otherwise defined, a baseline measurement is the last non-missing observation collected prior to the Delayed Start period. No between treatment p-values will be reported because (1) all patients received active treatment in the Delayed Start period, and (2) previous treatments in the Placebo-Controlled period were randomized at baseline and do not guarantee patients entering the Delayed Start period are without selection bias. Data summaries will include a total column and columns describing the treatments received across both study periods: 20mg, 50mg, PL/20 and PL/50.

When change from baseline is assessed, subjects will be included in the analysis only if both a baseline and a post-baseline measurement are available. Endpoint is the last non-missing post-baseline measurement. For analyses using last observation carried forward (LOCF), the last non-missing post-baseline measurement (scheduled or unscheduled) will be used to calculate change from baseline.

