6.6. Analysis Populations

For purposes of analysis, populations are defined in Table AZET.SAP.1.

Table AZET.SAP.1. Analysis Populations for Study I8D-MC-AZET

Population	Description	
Entered	All participants who sign informed consent	
Randomized	All entered patients who are randomized to study treatment.	
Evaluable – PC	All randomized patients with a baseline and at least one post-baseline scale result; only placebo-controlled visits included $(1-16)$	
Safety – PC	All randomized participants who take at least 1 dose of double-blind study treatment. Participants will be analyzed according to the treatment group to which they were randomized. Only placebo-controlled visits included $(1-16)$	
Safety – DS	All randomized participants who take at least 1 dose of double-blind study treatment. Participants will be analyzed according to the treatment group to which they were randomized. All visits included $(1-30)$	

Abbreviations: PC = Placebo-Controlled; DS = Delayed-Start

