6.13.2. Adverse Events

Adverse events will be summarized and compared across treatment groups in the Placebo-Controlled period and the entire study. Treatment-emergent adverse events (TEAEs) will be defined as those events that first occurred or worsened after the date of randomization (Visit 2).

Should there be insufficient data to make this determination (i.e., missing or incomplete AE start date, stop date, or time), the AE will be considered treatment-emergent. The treatment-emergent period ends on the last day of treatment plus 5 days (these 5 days constitute at least 5 half-lives of lanabecestat). Events occurring within the study but during a period of treatment interruption will only be treated as treatment-emergent if they occur within 5 days of the last dose prior to the treatment interruption.

The MedDRA lower-level term (LLT) will be used in the treatment-emergent computation. The maximum severity for each lower-level term (LLT) during the baseline period will be used as baseline.

An overview of AEs, including the number and percentage of patients who died, suffered serious adverse events (SAEs), discontinued due to AEs and who suffered TEAEs, will be provided. Comparison between treatments will be performed using Fisher's Exact Test.

Summaries of AEs by decreasing frequency of PT within SOC will be provided for the following:

- Preexisting condition
- TEAEs
- TEAEs by maximum severity
- TEAEs occurring in at least 2% of subjects by preferred term
- Serious AEs
- AEs reported as reason for study treatment discontinuation

These summaries will include number and percentages of subjects experiencing the events. Treatment comparisons will be carried out using Fisher's Exact Test. For TEAEs by maximum severity, Severity ="Severe" and "More Severe" will be combined into "Severe" category and the treatment comparison will be performed using Fisher's Exact Test.

All reported preexisting conditions and adverse events (with designations for TEAEs, SAEs, and discontinuations due to AEs) will be listed.

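### SAP 6.13.1 does not split exposure at the Week 78 switch, so the PL/20 and PL/50 totals include placebo days and no output gives those patients' days on LY3314814

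*SAP*

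**What the plan says.** SAP 6.13.1 (Extent of Exposure) gives one formula for every subject: "Days of exposure will be calculated for each subject: (Date of last dose – date of first dose + 1". The output is described in one further sentence: "Summary statistics will be presented for the total number of days of exposure by treatment". Neither sentence mentions the period, the product or the switch.

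The surrounding sections decide which patients and which data the formula meets:

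- SAP 6.13: "Safety presentations will be based on the Safety-PC and Safety-DS populations, as relevant".
- SAP 6.6: for the placebo-controlled populations, "only placebo-controlled visits included" (Visits 1-16). For Safety-DS, "All visits included" (Visits 1-30). Both safety populations require only randomization and one dose of blinded treatment, and both analyse patients by randomized group. Safety-DS does not require entry into the Delayed-Start period.
- SAP 6.1.1: Placebo-Controlled summaries have columns 20mg, 50mg and PLA, plus a total.
- SAP 6.1.2: for the Delayed-Start period, "Data summaries will include a total column and columns describing the treatments received across both study periods", namely 20mg, 50mg, PL/20 and PL/50.
- Protocol 7.1 and Table 7.1: patients on placebo move to LY3314814 20 mg or 50 mg at Visit 16 (Week 78).
- SAP 6.12.2.1: few patients have any Delayed-Start exposure, and safety is the only content from that period that will be summarized.

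**The concern.** In the 20mg and 50mg columns every dose is LY3314814, so time from first to last dose is time on the drug. In PL/20 and PL/50 the first dose is placebo, and a full first period adds 78 weeks of placebo before any LY3314814. One formula therefore produces two different quantities in adjacent columns of the same table, and the total column mixes them.

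A safety reader uses the exposure table to judge how long patients took the drug in which events were observed. The SAP reports adverse events as counts and percentages of subjects, so this table is the main guide to time on treatment. For the delayed-start sequences it would not show how much LY3314814 those patients received, and nothing else in the safety section does.

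Neighbouring sections do separate the periods. SAP 6.1.2 takes baseline as the last value before the Delayed-Start period, and SAP 6.13.3 gives an adverse event overview for each period. An exposure figure running from the first dose after Visit 2 does not match a Delayed-Start overview placed beside it.

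**Working it through.** The documents state no exposure figure, so there is nothing to reproduce. The check applies the SAP formula to an illustrative placebo-first patient.

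**Inputs**

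- Placebo-Controlled period: 78 weeks = 78 × 7 = 546 days (SAP section 4).
- Delayed-Start period: a further 78 weeks = 546 days (same place).
- Switch at Visit 16, Week 78 (Protocol 7.1).
- Assumed: daily dosing, no interruption, first dose on Day 1, first LY3314814 dose on Day 547. The stopping weeks are chosen for illustration.

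**Formulas**

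- SAP 6.13.1: last dose day − 1 + 1 = last dose day.
- LY3314814 days: last dose day − 547 + 1, or zero if the patient stopped by Day 546.
- Placebo share: placebo days ÷ SAP total.

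| Last dose at week | SAP total (days) | Placebo days | LY3314814 days | Placebo share | SAP total ÷ LY3314814 days |
|---|---|---|---|---|---|
| 52 | 364 | 364 | 0 | 100% | undefined |
| 78 | 546 | 546 | 0 | 100% | undefined |
| 82 | 574 | 546 | 28 | 95.1% | 20.5 |
| 104 | 728 | 546 | 182 | 75% | 4.0 |
| 156 | 1092 | 546 | 546 | 50% | 2.0 |

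For Week 104: 104 × 7 = 728; 728 − 547 + 1 = 182; 546 ÷ 728 = 75%; 728 ÷ 182 = 4.0.

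**Patients who never switched.** Safety-DS requires only one dose of blinded treatment and analyses by randomized group, so a placebo patient who stopped at Week 52 falls in PL/20 or PL/50 with 364 days of exposure and no LY3314814. Since SAP 6.12.2.1 says few patients reached the Delayed-Start period, such patients should be the majority in those two columns, and most of the days shown there would be placebo days. The documents give no counts, so this cannot be turned into a column mean.

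**Safety-PC.** With data limited to Visits 1-16, the PLA figure for these patients is at most 546 days and contains no LY3314814 days.

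**The case against.** The best defence is that PL/20 and PL/50 are sequence labels. SAP 6.1.2 defines the columns by what was received across both periods, and 6.13.1 speaks of exposure, not of LY3314814 exposure. Days from first to last dose are then the correct time on study medication for that sequence. This stands: the total is not an arithmetic error, and it misleads only if read as active-drug exposure. It leaves the gap open, however, because no other output gives LY3314814 days for these patients.

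It is also fair that little depends on the table. The study was stopped for futility, Delayed-Start summaries carry no between-treatment p-values, and few patients are involved after the switch.

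Two stronger readings are tempting, and the documents support neither:

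- **That LY3314814 days enter the PLA column.** Read alone, 6.13.1 would allow this, since a switched patient's last dose falls after Week 78. But PLA exists only in Placebo-Controlled summaries. SAP section 4 keeps the two periods apart, 6.1.1 ties those columns to treatment received in the first period alone, and 6.6 limits Safety-PC to Visits 1-16. What remains is a small wording gap: a visit window does not expressly truncate a last-dose date.
- **That interruptions must be subtracted to match the adverse event rule.** Protocol 8.1.2 says "The maximum permissible treatment suspension is a total of 6 weeks over the duration of the study", the exposure formula counts those days, and SAP 6.13.2 says "Events occurring within the study but during a period of treatment interruption will only be treated as treatment-emergent if they occur within 5 days", counted from the dose preceding the gap. The two rules do differ. But adverse events are reported as subject counts and percentages compared by Fisher's exact test, and no person-time rate is planned, so exposure days are not a denominator. First-to-last-dose duration is a legitimate definition, and subtracting gaps would be a preference.

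**Conclusion.** The point holds for the Delayed-Start columns. Following SAP 6.13.1 and 6.6 as written puts placebo days into the PL/20 and PL/50 exposure totals, gives positive exposure to placebo patients who never took LY3314814, and leaves the plan with no report of active-drug days for either sequence.

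For a placebo-first patient with a full first period, the total is 20.5 times the LY3314814 days if dosing stops at Week 82, 4.0 times at Week 104 and 2.0 times at Week 156. These ratios assume uninterrupted daily dosing and a switch exactly at Week 78. They are illustrations per patient, and the effect on the real table cannot be computed from the documents.

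The consequence is confined to the description of exposure that accompanies the Delayed-Start safety data. No efficacy conclusion, p-value or Placebo-Controlled comparison depends on it. A clarification is worth making because safety is all that will be summarized from that period.

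**What to change.** Amend SAP 6.13.1 as follows:

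1. For PL/20 and PL/50 in Safety-DS, report LY3314814 days as last dose date − first post-switch dose date + 1, set to zero for patients who never switched.
2. Show placebo days for these two columns separately. The sequence total may be kept if it is labelled as time on study medication.
3. State that Safety-PC exposure ends at the last Placebo-Controlled dose. This only makes explicit what 6.1.1 and 6.6 already imply.

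The 20mg and 50mg columns need no change. The cost is SAP wording and minor programming. The switch can be located from the Visit 16 dispensing shown in Protocol Table 2.2, so no new data collection should be needed. If the first post-switch dose date is not recorded directly, the SAP should say how it is derived from that dispensing record.

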6.13.2. Adverse Events

Adverse events will be summarized and compared across treatment groups in the Placebo-Controlled period and the entire study. Treatment-emergent adverse events (TEAEs) will be defined as those events that first occurred or worsened after the date of randomization (Visit 2).

Should there be insufficient data to make this determination (i.e., missing or incomplete AE start date, stop date, or time), the AE will be considered treatment-emergent. The treatment-emergent period ends on the last day of treatment plus 5 days (these 5 days constitute at least 5 half-lives of lanabecestat). Events occurring within the study but during a period of treatment interruption will only be treated as treatment-emergent if they occur within 5 days of the last dose prior to the treatment interruption.

The MedDRA lower-level term (LLT) will be used in the treatment-emergent computation. The maximum severity for each lower-level term (LLT) during the baseline period will be used as baseline.

An overview of AEs, including the number and percentage of patients who died, suffered serious adverse events (SAEs), discontinued due to AEs and who suffered TEAEs, will be provided. Comparison between treatments will be performed using Fisher's Exact Test.

Summaries of AEs by decreasing frequency of PT within SOC will be provided for the following:

- Preexisting condition
- TEAEs
- TEAEs by maximum severity
- TEAEs occurring in at least 2% of subjects by preferred term
- Serious AEs
- AEs reported as reason for study treatment discontinuation

These summaries will include number and percentages of subjects experiencing the events. Treatment comparisons will be carried out using Fisher's Exact Test. For TEAEs by maximum severity, Severity ="Severe" and "More Severe" will be combined into "Severe" category and the treatment comparison will be performed using Fisher's Exact Test.

All reported preexisting conditions and adverse events (with designations for TEAEs, SAEs, and discontinuations due to AEs) will be listed.

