## Study Schedule, Protocol I8D-MC-AZET, Visit 17 through Visit 30 (Delayed-Start Period) Abbreviations and Footnotes

Abbreviations: ADAS-Cog = 13-item Alzheimer's Disease Assessment Scale-Cognition; ADCS-ADL = The Alzheimer's Disease Cooperative Study Activities of Daily Living Inventory; Aβ = A-beta amyloid; CDR = Clinical Dementia Rating; CSF = Cerebrospinal fluid; C-SSRS = Columbia Suicide Severity Rating Scale; ECG = Electrocardiogram; ED = early discontinuation; EQ-5D Proxy = 5-dimensional EuroQol quality of life scale; FAQ = Functional Activities Questionnaire; FDG = fludeoxyglucose; F/U = Follow-up; LP = lumbar puncture; MMSE = Mini-Mental State Examination; MRI = Magnetic resonance imaging; NPI = Neuropsychiatric Inventory; PET = Positron emission tomography; PK = Pharmacokinetic; QoL-AD = Quality of Life in Alzheimer's Disease; RBANS = Repeatable Battery for the Assessment of Neuropsychological Status; RNA = ribonucleic acid; RUD-Lite = Resource Utilization in Dementia-Lite.

- Every effort should be made for visits to occur on the designated study days. The overall treatment period in the protocol should be maintained (that is, visits should be scheduled based on the baseline visit rather than the previous visit). Study procedures designated for a specific visit should be performed within 1 day whenever possible. If the time spent at the site needs to be minimized, the assessments can be completed over a longer period.
- All patients who discontinue study treatment before Visit 30 (Week 156) should have Early Discontinuation (ED) procedures and assessments performed as soon as possible. ADCS-ADL, FAQ, CDR, MMSE, RBANS, ADAS-Cog13, and NPI tests should be conducted at the early discontinuation visit if it has been more than 12 weeks since they were last administered. Florbetapir amyloid PET, MRI and lumbar puncture, should only be performed if it has been at least 24 weeks since the previous assessment. If both MRI and LP are being done, the MRI should be completed prior to the LP (See FDG-PET or AV-1451 [Tau] PET addendum if applicable).
- c Follow-up should be scheduled to occur 4-6 weeks after the last dose of investigational product.
- Visit 23 and 27 (Week 110 and 136) will be conducted by telephone and may include either the patient or the study partner, or both, as appropriate and the patient or study partner may be required to visit the clinic within ±1 week of the visit for drug dispensing.

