5.1. Summary of Study Design

[figure not shown]
Study I8D-MC-AZET (AZET) is an international, multicenter, randomized, parallel-group, 78 week double-blind (DB), placebo-controlled study of 2 fixed dose levels of LY3314814 (20 mg or 50 mg) in patients with mild AD dementia and abnormal levels of amyloid, followed by a 78 week Delayed-Start period.

Study AZET is the second Phase 3 study that was initiated after a safety interim analysis of an ongoing Phase 2/3 study [I8D-MC-AZES] in an early AD (mild cognitive impairment [MCI] due to AD and mild AD dementia) population. Study AZET will only enroll patients with mild AD. This study is 18 months (78 weeks) in duration for the primary outcome. Studies of this duration, in mild AD dementia patients, are believed to be of sufficient length to detect a difference from the placebo decline rate (Liu-Seifert et al. 2015).

The purpose of the Delayed-Start period of AZET is to assess whether LY3314814 has an effect independent of acute symptomatic effects otherwise consistent with disease modification or slowing of disease progression. In other words, the objective of the Delayed-Start period is to determine if the patients originally randomized to receive placebo and switched to LY3314814 at the start of the Delayed-Start period could achieve the same outcome after receiving 6 months of active therapy (at Week 104) as patients originally randomized to receive LY3314814 in the double-blind period. This objective will be evaluated using all available data through Week 104 by the time of database lock of the Placebo-Controlled period. After the study was stopped for futility, all ongoing patients were asked to come in for a futility-based discontinuation visit. Patients at this visit followed the schedule of events for an early discontinuation visit.

Figure AZET.SAP.1 illustrates the study design.

Figure AZET.SAP.1 Illustration of Study Design for Clinical Protocol I8D-MC-AZET.

Abbreviations: LY=LY3314814

^{*}At Visit 2, patients randomized to placebo in the Placebo-Controlled period will also be randomly assigned to a Delayed-Start treatment group to begin at Week 78. This will be achieved by randomizing patients to one of four

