6.13.3. Deaths, Other Serious Adverse Events, and Other Notable Adverse Events

Overviews of adverse events will be presented for the Placebo-Controlled period and the Delayed-Start period, respectively, including within each period the number and percentage of subjects who died, experienced serious adverse events, experienced adverse events leading to study discontinuation, and experienced treatment-emergent adverse events. Treatment groups will be compared in the Placebo-Controlled period using Fisher's Exact Test.

Events of the major adverse cardiovascular event type (MACE) that are blindly evaluated by external independent consultants will be summarized and listed.

In addition, the proportion of subjects within specific clusters of TEAEs will be summarized and treatment comparisons will be conducted using Fisher's Exact Test. Clusters will be created from MedDRA High Level Group Terms (HLGTs) and MedDRA SMQ's.

 Table AZET.SAP.2.
 Adverse Events of Special Interest

AE Groups of Interest (Clusters)	MedDRA High Level Group Terms (HLGTs)
Nervous System Disorders	Neuromuscular Disorders HLGT
	Demyelination SMQ
	Peripheral Neuropathy SMQ
Eye Disorders	Retinal disorders SMQ
Skin Disorders	Sub-group A:
	Epidermal and Dermal Conditions HLGT (excluding sub-group B terms)
	Sub-group B (Hypopigmentation-related events):
	Hypopigmentation disorders HLT
	Pigmentation changes, NEC HLT
	Preferred terms: 'hair depigmented', 'eyelash discolouration', 'iris hypopigmentation', 'eye colour change', 'lip colour altered', 'lip discolouration', 'hair colour changes', 'achromotrichia aquired', 'poliosis'
Liver Disorders	Drug related hepatic disorders - comprehensive search SMQ
Cardiovascular-type events – Arrhythmic	Arrhythmia related investigations, signs and symptoms SMQ
	Cardiac arrhythmia terms (incl bradyarrhythmias and tachyarrhythmias) SMQ
	TdP/QT prolongation SMQ
Cardiovascular-type events - Ischemic	Ischaemic heart disease SMQ
Cardiovascular-type events - Stroke	Central nervous system vascular disorders SMQ
Cardiovascular-type events – including orthostatic hypotension	Decreased and Nonspecific Blood Pressure Disorders and Shock HLGT

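### The 5-day treatment-emergent cut-off can drop skin and eye findings first dated at a late discontinuation or close-out examination from the tested special-interest clusters

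*SAP*

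**What the plan says.** SAP 6.13.2 (Adverse Events) fixes the end of the window: "The treatment-emergent period ends on the last day of treatment plus 5 days". The reason given is that "these 5 days constitute at least 5 half-lives of lanabecestat". Events during a treatment interruption "will only be treated as treatment-emergent if they occur within 5 days of the last dose prior to the treatment interruption". Where dates are missing or incomplete, "the AE will be considered treatment-emergent".

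SAP 6.13.3 then says that "the proportion of subjects within specific clusters of TEAEs will be summarized", with Fisher's exact test between groups. Table AZET.SAP.2 lists the clusters. They include retinal disorders and, under skin, a hypopigmentation sub-group. Neither section makes an exception for skin or eye events.

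On timing, protocol Table 2.2 schedules the eye examination at Weeks 52 and 78 and at early discontinuation (ED), and the skin examination at Weeks 13, 52 and 78 and at ED. Its ED footnote asks for the ED procedures promptly after treatment stops, without a limit in days. After the futility stop, SAP 5.1 reports that "all ongoing patients were asked to come in for a futility-based discontinuation visit" and that this visit used the ED schedule. It gives no timing relative to the last dose. The protocol's Table 2.3 footnote adds: "Follow-up should be scheduled to occur 4-6 weeks after the last dose of investigational product".

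**The concern.** A half-life rule suits effects that appear and are noticed while drug is in the body. Pigment and retinal changes are different in one respect: this trial looks for them mainly at scheduled specialist examinations that are months apart. Protocol 3.3 names hypopigmentation, rash and retinal changes as potential risks, and protocol 9.4.9.1 makes eye and skin effects events of special interest.

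If such a change develops on drug but is first seen, and given its onset date, at an examination 6 or more days after the last dose, it is not a treatment-emergent event and does not enter the cluster. The futility stop makes this more pressing, because all ongoing patients were asked to attend an ED-type examination at about the same point in the trial's life. At stake is how completely the between-arm skin and eye comparison captures what the examinations found.

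**Working it through.** **1. The plan's own figure.** The 5 days are said to be at least 5 half-lives. Neither document gives a half-life, so this cannot be reproduced. It implies only a half-life of at most 5/5 = 1 day.

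**2. The rule set against the schedule.**

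| Source | Content | Consequence |
|---|---|---|
| SAP 6.13.2 | Window closes on day 5 after last dose | Onset on day 6 or later is not treatment-emergent |
| SAP 6.13.3 | Clusters count treatment-emergent events only | The same events are absent from the tested row |
| Protocol Table 2.2 and ED footnote | Skin and eye examinations at ED; no day limit | The examination may fall on day 6 or later |
| SAP 5.1 | Close-out visit follows the ED schedule; no link to last dose | The same exposure for patients ongoing at the stop |
| Protocol 9.4.7 and 9.4.8 | Clinically significant findings that lead to a diagnosis are recorded as a pre-existing condition or an adverse event; no rule for dating onset | Onset may be dated to the examination |

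Exclusion needs two conditions together: an examination on day 6 or later, and a complete onset date falling after day 5.

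**3. Who is exposed.** A patient stopped before Week 52 has one scheduled post-baseline eye examination, the ED visit. Planned dropout in the Placebo-Controlled period is 25% (SAP 5.2), so the planned number of ED visits is 0.25 × 1899 ≈ 475, or 0.25 × 633 ≈ 158 per arm. Patients closed out by the futility stop come on top, and their number is not given. These are counts of visits, not of excluded findings.

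**4. Follow-up visit.** It falls 28–42 days after the last dose, which is 28 − 5 = 23 to 42 − 5 = 37 days after the window closes. Table 2.3 records adverse events there but schedules no skin or eye examination. Only reported events or unscheduled examinations are affected.

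**5. Interruptions.** The same cut applies, and the protocol allows this much time off drug: "The maximum permissible treatment suspension is a total of 6 weeks over the duration of the study". In a single 42-day interruption, up to 42 − 5 = 37 days lie outside the window.

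**6. What an equal loss would do.** The denominator of 633 per arm reproduces from SAP 5.2: 554/(1 − 0.25 × 0.50) = 633.1. Event rates are not in the documents. The true rates below, and the fraction f of events cut in every arm, are assumptions. The observed rates become p(1 − f). With d the difference between them and p̄ their mean, at two-sided 0.05 (protocol 10.3.4):

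power = Φ{[d − 1.96·√(2p̄(1 − p̄)/n)] / √([p₀(1 − p₀) + p₁(1 − p₁)]/n)}

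| f | 1% vs 3%: difference | power | 1% vs 4%: difference | power |
|---|---|---|---|---|
| 0 | 2.0 points | 72% | 3.0 points | 93% |
| 10% | 1.8 | 67% | 2.7 | 90% |
| 20% | 1.6 | 62% | 2.4 | 86% |
| 30% | 1.4 | 56% | 2.1 | 81% |
| 50% | 1.0 | 43% | 1.5 | 67% |

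The risk ratio stays at 3 or 4 throughout. This is the normal approximation; the planned test is Fisher's exact.

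**The case against.** The SAP rule turns on when an event began or worsened, not on when it was seen. No passage says that sites date onset to the examination day, and an incomplete date keeps the event in. That is right, and it means exclusion is possible rather than automatic. It does not help a finding that carries a complete date.

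The close-out examinations may have been prompt. If patients were dosed until about the visit, none would be affected. That also stands: the documents neither show delay nor rule it out.

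Skin is seen more often than its dedicated schedule suggests. Protocol 9.4.3 includes skin in both the full and the brief physical examination, which Table 2.2 places at Weeks 4, 13, 26, 39, 52, 65 and 78 and at ED. Patients with visual complaints are referred for unscheduled evaluation (protocol 9.4.7). The sole-examination argument therefore applies only to scheduled eye examinations in patients stopped before Week 52.

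The findings are not lost from the report. All adverse events are listed, and SAP 6.13.8.2 and 6.13.8.3 summarize new skin and eye findings without the 5-day rule. This is a real mitigation, but a partial one: those summaries refer to findings *during treatment* without defining the term, and they name no between-group test.

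Finally, SAP 6.1 says that no test in the stopped study will be read as significant. This limits the consequence. The cluster proportions will still be reported, and safety remains an objective (SAP 4.5).

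**Conclusion.** The gap is real but narrow. A skin or eye finding with onset fully dated to an ED or close-out examination 6 or more days after the last dose is left out of the tested cluster comparison, even if it arose on drug. This rests on two things that the documents leave open: how long after the last dose these examinations took place, and how onset was dated. The number of patients affected cannot be derived, and the power figures above are illustrations at assumed rates.

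Three stronger readings are tempting and are not supported:

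- **That the rule biases the comparison toward no harm differentially.** No difference between arms in visit timing or dating is documented. Equal proportional loss leaves the risk ratio unchanged and lowers the risk difference and the power.
- **That only 12–18% of post-dose events are captured.** The ratios 5/42 = 11.9% and 5/28 = 17.9% are shares of days between last dose and follow-up, not shares of events.
- **That skin and eye examinations at the 4–6 week follow-up are discarded.** None is scheduled there.

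This does not undermine the safety analysis as a whole. A supplementary summary is worth adding because it is cheap and guards against missing changes that were detected late.

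**What to change.** Keep the 5-day window as the main definition for all treatment-emergent tables. Then, in the SAP:

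1. Add a supplementary row for the Eye and Skin clusters in Table AZET.SAP.2. It counts events new or worsened from first dose through the ED or close-out examination and the follow-up visit. For patients who enter the Delayed-Start period, end the Placebo-Controlled count at the first Delayed-Start dose.
2. For that row, treat a finding first seen at the ED or close-out examination as treatment-emergent unless there is evidence that it began after the 5-day window.
3. Use the same cut-off to define *during treatment* in SAP 6.13.8.2 and 6.13.8.3, so that the examination summaries and the supplementary row agree.

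The cost is SAP wording and two extra cluster rows, with no new data. The downside is that a few off-drug background events are added in all arms, which slightly dilutes the contrast. Showing the row beside the main one makes that visible.
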